The goal of the present exploratory investigation is to see if there is a suggestion of a large additive or synergistic effect of melatonin and donepezil given together. Individually both medications improve sleep, but appear to do so in different ways, with melatonin altering circadian rhythm and donepezil altering the characteristics of REM sleep. In this pilot investigation we will examine whether their combined effects on sleep lead to a large improvement in the behavior of children with ASD. Combined pharmacotherapy is very common in clinical practice, but is rarely studied in research (Comer et al. 2010). These two medications are both well tolerated and there is no negative drug interaction between the two. This investigation will use an RCT as well as a set of exploratory analyses to assess the combined effects of

these two medications compared to placebo in terms of behavioral and sleep measures. In addition we will collect exploratory biomarkers (e.g., digit ratio, the ratio of the lengths different fingers as a measure of the balance of sex hormones during embryonic development) to relate to the various sleep and behavioral measures. A positive signal from this study may be used to guide a follow-up study with greater numbers of study subjects and statistical power.

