### Study Design

**Table 1 – Study design and medication dosage (mg)**

Week			Run-In (V0-V1)	Phase 1 (V1-V2)					Phase 2 (V2-V3)					Wash- Out (V3-V4)	
				1 - 5	6	7	8	9	10	11	12	13	14	15	
Group A	Younger*	Donepezil	P	1.25	2.5	2.5	2.5	2.5	2.5	1.25	2.5	2.5	2.5	2.5	
		Melatonin	P	3	3	3	3	3	3	3	3	3	3	3	
	Older	Donepezil	P	2.5	5.0	5.0	5.0	5.0	5.0	2.5	5.0	5.0	5.0	5.0	
		Melatonin	P	3	3	3	3	3	3	3	3	3	3	3	
Group B	Younger*	Donepezil	P	P	P	P	P	P	P	1.25	2.5	2.5	2.5	2.5	
		Melatonin	P	P	P	P	P	P	P	3	3	3	3	3	
	Older	Donepezil	P	P	P	P	P	P	P	2.5	5.0	5.0	5.0	5.0	
		Melatonin	P	P	P	P	P	P	P	3	3	3	3	3	

Key: \* Younger = children below 12 years of age or 80 lbs. weight, who start and end at a lower dose of donepezil, than the other Older children; P = Placebo

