**Table 2 – Visit procedures**

Visit no.	Person in charge	Screening	Baseline (V0)	V1	V2	V3	V4
Study weeks		/	0	5	10	15	17 – 27
Incl/excl criteria*	[name]	X					
Pregnancy test (if applicable)**	CRC nurse	X					
Informed consent and assent	Study coordinator	X					
Aberrant Behavior Checklist	Parent		X	X	X	X	X
Child's Sleep Habits Questionnaire	Parent		X	X	X	X	X
Parent Global Impressions	Parent		X	X	X	X	X
Prenatal, developmental, neurological history	[name]		X				
Neurological exam	[name]		X	X	X	X	X
Clinical Global Impressions	[name]		X	X	X	X	X
Adverse event monitoring	[name]			X	X	X	X
Head circumference	CRC nurse		X				
D2/D4 finger length ratio	CRC nurse		X				
Dispense study drug	[name]		X	X	X		
Sleep hygiene education	[name]		X				
Study drug accountability	Study coordinator			X	X	X	

\*Includes renal/hepatic function test if blood work was not done within the past month

\*\* For female patients who have started menses

Patients will meet with [name] for 5 visits (baseline, follow up visit 1-4) every 5 weeks:

**Phase 1** (between follow up visit 1 and 2) – The investigation will be conducted in 2 Phases as shown in Table 1. Phase 1 will be a double-blind randomized clinical trial using a parallel group design. It will assess the combined benefit of donepezil and melatonin in Group A versus placebo in Group B over 5 weeks.

**Phase 2** (between follow up visit 2 and 3) – Phase 1 will be followed by an exploratory Phase 2 in which both groups (A & B) will be placed on the active medications for an additional 5 weeks. Phase 2 will allow us to explore whether Group A derives any additional benefit from 5 extra weeks of treatment with the active medications, and whether Group B obtains any benefit from switching from placebo to the active medications.

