#### **Treatment**

**Melatonin**– Melatonin is categorized by the US Food and Drug Administration (FDA) as a dietary supplement. It is widely available in the US without prescription. The dose of melatonin will be fixed at 3 mg for all participants, a level well tolerated in previous studies in this population of children (Tordjman et al. 2013). Adverse effects of melatonin have been found to be minimal to none in twenty small treatment studies in ASD (Rossignol and Frye 2013; Tordjman et al. 2013). None of the seven placebo-controlled trials of melatonin have found any increased risk of side effects (McArthur and Budden 1998; Garstang and Wallis 2006; Wasdell et al. 2008; Wirojanan et al. 2009; Wright et al. 2011; Cortesi et al. 2012; Gringras et al. 2012; Tordjman et al. 2013). Most other small studies of children with ASD taking melatonin also report no side effects (Jan et al. 1994; Horrigan and Barnhill 1997; Hayashi 2000; Jan et al. 2004; Gupta and Hutchins 2005; Giannotti et al. 2006; Galli-Carminati et al. 2009; Tordjman et al. 2013). Side effects, when noted in the other ASD melatonin studies tended to be mild and included: tiredness, daytime sleepiness, fogginess, awakening in the middle of sleep, excitement after awakening and before going to sleep, headaches, bed-wetting, and diarrhea (Ishizaki et al. 1999; Paavonen et al. 2003; Andersen et al. 2008; De Leersnyder et al. 2011; Malow et al. 2012; Tordjman et al. 2013). Dose timing is important for melatonin, and in keeping with earlier investigations (Wasdell et al. 2008; Wirojanan et al. 2009; Wright et al. 2011), parents/legal guardians will be instructed to administer it (12 ml) 30 minutes before a consistent desired bedtime. We will use supplemental melatonin in liquid form (Natrol®) as used in a previous study that obtained IND approval from the FDA for use in children with autism (Malow et al. 2012).

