**Donepezil**– Donepezil, which is regulated by the FDA as a pharmaceutical drug, is also well tolerated in this population (Hardan and Handen 2002; Chez et al. 2003; Buckley et al. 2011; Handen et al. 2011; Srivastava et al. 2011). Related studies using other acetylcholinesterase inhibitors, including rivastigmine (Chez et al. 2004) and galantamine (Ghaleiha et al. 2013) have also shown that this class of medications is well tolerated in ASD children. Studies of donepezil in related pediatric clinical populations, such as fragile X (Sahu et al. 2013) and general Pervasive Developmental Disorder (Doyle et al. 2006) have found similar levels of tolerance. To maximize tolerance, the dosage will be titrated, as is commonly done in clinical trials with autistic children (Hardan and Handen 2002; Buckley et al. 2011; Handen et al. 2011). Parents/legal guardians will be instructed to administer the donepezil (1 capsule) with the melatonin, 30 minutes before a consistent desired bedtime.

**Drug compounding** –Pine Pharmaceuticals will repack the liquid melatonin from Natrol® and compound the liquid placebo. The Stony Brook Pharmacy will repack 5 mg generic donepezil into 1.25 and 2.5 mg gelatin capsules and compound the placebo in identical gelatin capsules. Patients will be given 40 days’ worth of study medication.

**Treatment Randomization** – Patients who agree to participate after they pass the screening will be assigned a study ID. After the run-in phase, study subjects will be randomly assigned to Group A or B using a computer-generated randomization plan with blocking and stratification by gender and age group (Younger: children below 12 years of age or 80 lbs. weight; Older:  $\geq$  12 years or  $\geq$  80 lbs.).

**Treatment Blinding** – The study pharmacists at Stony Brook and at Pine Pharmaceuticals will be the only individuals informed of the randomization assignments and will be responsible for labeling study drug and maintaining a master list linking patients with treatment assignments. All other research staff and participants will be masked regarding treatment assignment. Masking of active and placebo treatments will be preserved by creating liquids and capsules and containers that appear identical.

**Study Medication Accountability** – Study medication used and unused will be monitored through a drug accountability form completed at visit 1, 2, and 3.

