### ***Analysis***

**Power** – This is an exploratory study. It will be powered only to detect a large superiority ( $d = 0.9$ ) of the combined medication treatment as compared to placebo on the primary outcome (ABC-Social) in Phase 1 of the study. With a proposed sample size of 60 (30 in each group) and 10% subject attrition, there will be 54 completers (27 in each group), and power is estimated to be 91.1% (2-sided test, 5% type 1 error rate)

**Statistical Analysis** - All statistical analyses will be performed according to an intention-to-treat principle on the full sample. A last-observation-carried-forward imputation strategy will be used for missing data. The primary analysis will consist of an independent samples *t*-test on the normally distributed ABC Social change score in Phase 1. This will be followed by an analysis of covariance (ANCOVA) controlling for any variables on which the two drug groups are found to differ at baseline. Analyses of other continuous outcome variables in Phase 1 will use a similar approach. Group differences on categorical outcomes (e.g., CGI) will be analyzed by Chi Square test. Exploratory analyses for within group changes in Phase 2 (e.g., testing whether Group A derives additional benefit from 5 extra weeks of active treatment, or whether Group B obtains any benefit from the change from placebo to active treatment) and during the Washout Phase (e.g., testing whether the effects of the medications do washout when withdrawn) will be analyzed by means of a paired sample *t*-test on the outcome variables of interest. All tests will be 2-tailed, with a  $p = .05$  considered significant, with no correction for multiple analyses in this exploratory study. Correlation coefficients will be used to explore the relation of biomarkers to baseline behavioral and sleep measures, again using  $p = .05$ . All analyses will be performed using SPSS 21.0 statistical software. There will be no interim analysis.

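### The randomisation strata, one of which also sets the donepezil dose level, enter no planned Phase 1 model, and no descriptive estimate by dose group is planned

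*Combined protocol and SAP*

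**What the plan says.** **Dosing.** In the Group A rows of Table 1 (Study Design), Younger children get donepezil 1.25 then 2.5 mg and Older children 2.5 then 5.0 mg. The table key says that Younger children "start and end at a lower dose of donepezil, than the other Older children". Melatonin does not vary: "The dose of melatonin will be fixed at 3 mg for all participants" (Treatment, Melatonin paragraph).

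**Randomisation.** The Treatment Randomization paragraph specifies a "computer-generated randomization plan with blocking and stratification by gender and age group". The age group there is the Younger/Older group of Table 1.

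**Declared comparison.** The Phase 1 paragraph below Table 2 states: "It will assess the combined benefit of donepezil and melatonin in Group A versus placebo in Group B over 5 weeks".

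**Analysis.** The Statistical Analysis paragraph says: "The primary analysis will consist of an independent samples" *t*-test, Group A against Group B, on the Phase 1 change in ABC-Social. An ANCOVA follows, "controlling for any variables on which the two drug groups are found to differ at baseline". Other continuous Phase 1 outcomes are handled similarly. No stratum term, estimate by stratum or arm-by-stratum analysis is planned.

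**Purpose.** The Background says: "A positive signal from this study may be used to guide a follow-up study".

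**The concern.** The design treats the Younger/Older group as important enough to fix the dose level and to balance the arms on it. The analysis does not use it. The one route by which it could enter, the follow-up ANCOVA, selects covariates by observed imbalance, and stratified blocking exists to prevent that imbalance.

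Two things are at stake:

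- **Precision.** When arms are balanced on a factor that is related to outcome, an unadjusted *t*-test leaves the between-stratum variation in the error term, although the balance has removed it from the treatment difference. The standard error is then too large.
- **Information for the next study.** A follow-up has to specify an age range and a donepezil dosing plan. The planned output is a single pooled number, with nothing on whether the two dose groups point the same way.

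**Working it through.** **1. Inputs.** From the Power paragraph: d = 0.9, 27 completers per arm, two-sided 5%, stated power 91.1%. The documents give neither the Younger/Older mix nor any difference in mean change between the strata. Both are assumed below, in units of the within-stratum SD (set to 1).

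**2. The plan's own figure.** Normal approximation: power = Φ(0.9 × √(27/2) − 1.96) = Φ(3.307 − 1.960) = Φ(1.347) = 91.1%, which matches. The noncentral *t* gives 90.1%, so about 90% is the reference below.

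**3. Standard error when the stratum is left out.** Let a share p of each arm be in one stratum, and let mean change differ between strata by δ. The within-arm variance seen by the *t*-test is about 1 + p(1 − p)δ², whereas the balanced treatment difference varies as if the variance were 1. The ratio of the reported to the correct standard error is therefore √(1 + p(1 − p)δ²).

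| Mix | δ = 0.5 | δ = 1.0 |
|---|---|---|
| 50:50 | √1.0625 = 1.03 | √1.25 = 1.12 |
| 75:25 | √1.0469 = 1.02 | √1.1875 = 1.09 |

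A 50:50 mix is the worst case.

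**4. Error rate and power.** Simulation with 27 per arm, arms balanced within stratum, an approximately 50:50 mix (14 and 13 per arm) and 40,000 replicates per setting:

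| δ (assumed) | Type I error, *t*-test | Power at d = 0.9, *t*-test | Power at d = 0.9, with stratum factor |
|---|---|---|---|
| 0 | 5.1% | 90.0% | 89.9% |
| 0.3 | 4.8% | 89.6% | 90.0% |
| 0.5 | 4.2% | 89.1% | 90.2% |
| 0.8 | 3.6% | 87.2% | 90.4% |
| 1.0 | 2.9% | 85.3% | 90.2% |

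With the factor in the model, type I error stays at about 5% throughout. The unstratified test is conservative, not biased, and loses 0 to 5 points of power.

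**5. What an estimate by dose group could show.** The 95% CI half-width within a stratum is t × √(2/n):

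- n = 13 per arm: 2.064 × √(2/13) = 0.81 SD
- n = 14 per arm: 2.056 × √(2/14) = 0.78 SD

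For the arm-by-stratum difference, SE = √(2/14 + 2/13) = 0.545, so the half-width is 2.009 × 0.545 = 1.09 SD. Power to detect an arm-by-stratum difference of 0.9 SD is 30% to 37% across mixes from 75:25 to 50:50. These are estimates to display, not tests to rely on.

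**The case against.** The strongest defence is that the plan already answers the question it asks. The declared comparison is Group A against Group B. Each stratum has its own concurrently randomised placebo children, so the pooled difference is a valid weighted average. The study is declared exploratory and is powered only for a large overall effect. All of this stands.

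Three further objections:

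- **The outcome is a change score**, which already removes stable level differences between age groups. No document supports a 0.5 to 1.0 SD difference in change. That also stands, so the precision loss is a range under assumption and may be close to nil.
- **Dose is set by age and weight, not randomised.** The twofold ratio is in mg. No weights are given, so the ratio per kg is unknown. An estimate by stratum cannot separate dose from age or weight. This limits what the estimate means, but not the value of showing it.
- **The plan is only exploratory.** This is a weaker defence, because the same paragraph does pre-plan exploratory Phase 2, washout and biomarker analyses.

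A reader might infer two stronger claims. The first is that a positive result would belong to neither regimen. It would not be specific to one regimen, but it would be interpretable as the average effect of the dosing plan.

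The second is that pooling sharply cuts power. If one stratum has d = 0.9 and the other exactly 0, the pooled test has power of about 16%, 34% or 59% with 30%, 50% or 70% of children in the responding stratum. Nothing in the documents supports a null stratum, and the loss reflects a smaller average effect, not an analysis error. Simulating that scenario with 8, 14 or 19 of 27 per arm in the responding stratum gives power of 14%, 35% and 60% for the *t*-test and 15%, 37% and 61% with the stratum factor, a recovery of 0 to 2 points.

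**Conclusion.** The point holds as a minor one. The stratification factors are in no planned Phase 1 model, and the rule for choosing covariates would rarely bring them in.

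The consequence is a mildly conservative primary test. For an assumed 0.5 to 1.0 SD difference in mean change between Younger and Older children at a 50:50 mix, the standard error is about 3% to 12% too large, type I error is about 4% to 3%, and power at d = 0.9 is about 89% to 85% instead of about 90%. With no such difference, nothing is lost. The gender stratum was not quantified; the same formula applies.

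Separately, the planned output cannot show whether the effect is similar in the two dose groups. A stratum estimate would be imprecise (half-width about 0.8 SD) and confounded with age and weight, so it could inform the follow-up only descriptively. The validity of the pooled Group A against Group B comparison is not in question.

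**What to change.** In the Statistical Analysis paragraph:

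1. Make the primary Phase 1 ABC-Social analysis a linear model of the change score on treatment arm, with the randomisation strata (Younger/Older group and gender) as fixed factors, whatever the observed baseline balance. Use the same factors for the other continuous Phase 1 outcomes.
2. Report the Phase 1 treatment difference with a 95% CI separately for Younger and Older children, together with the arm-by-stratum estimate and its CI. Label these descriptive, and state that dose is confounded with age and weight and that the intervals will be wide.

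Use the stratum recorded at randomisation. As worded in the Treatment Randomization paragraph, the two definitions overlap: age and weight are joined by an *or* on both sides, so a child under 12 who weighs 80 lbs or more fits both. The definitions must be reconciled before the factor can be coded.

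The cost is SAP wording and one extra table, with no new data, visits or patients. The factors use two degrees of freedom. Adding the Younger/Older factor alone left simulated power at about 90% even when the strata did not differ.

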**Run-In Phase** (between visit 0/baseline and 1) – Phase 1 will be preceded by a Run-In Phase of 5 weeks where all subjects will receive placebo and instructions about how to improve sleep hygiene using the “Good Sleep Habits Checklist” (Durand 2014). Subjects and their families will be blinded to treatment during this phase, but investigators will not. The run-in will allow us to assess patient compliance with the study protocol. Only those who achieve compliance of at least 80% will be allowed to continue in the study and then be randomized to the two Groups. The Run-In will also allow us to control for any improvement due to better sleep hygiene. Finally, the Run-In will allow us to control for placebo effects, because the score obtained at the end of Run-In (possibly reflecting placebo effects) will be used as a baseline to which the scores at the end of each treatment phase can be compared.

**Wash-Out Phase** (between follow up visit 3 and 4) – A washout period of between 2 – 12 weeks will follow Phase 2, allowing us to explore any changes in both subject groups after active treatment has been withdrawn. The length of this period will vary in order to coincide with the next clinical visit of the patient with [name], recognizing that this data is of lower priority.

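### The primary ABC-Social test fixes the V1 slope at 1 instead of adjusting for V1, and the supporting ANCOVA chooses its covariates only after baseline data are seen

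*Combined protocol and SAP*

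**What the plan says.** The Statistical Analysis paragraph of the Analysis section states: "The primary analysis will consist of an independent samples" t-test "on the normally distributed ABC Social change score in Phase 1". It is followed by an "analysis of covariance (ANCOVA) controlling for any variables on which the two drug groups are found to differ at baseline". The other continuous Phase 1 outcomes are to be handled in the same way. Analyses follow an "intention-to-treat principle on the full sample", and "A last-observation-carried-forward imputation strategy will be used for missing data".

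The Run-In Phase paragraph under Study Design identifies the starting point of the change score: "the score obtained at the end of Run-In (possibly reflecting placebo effects) will be used as a baseline". That is V1, so the Phase 1 change is V2 minus V1. Table 2, however, gives the label Baseline to V0. Its "Aberrant Behavior Checklist" row is marked at V0 to V4 only, so there is no ABC measurement between V1 and V2.

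Treatment Randomization uses blocking and "stratification by gender and age group". No section names V1 ABC-Social, gender or age group as a fixed covariate in any analysis.

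**The concern.** There are two weaknesses.

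- **Precision.** Subtracting V1 uses the baseline, but with its coefficient set to 1. ANCOVA estimates that coefficient. Unless the true slope is close to 1, the change score carries extra variance from V1 that the trial could remove at no cost.
- **Prespecification.** The ANCOVA that follows does not make up for this. V1 enters only if the arms happen to differ on it. The plan gives no list of candidate variables, no criterion for a difference and no visit for the check, and the word baseline is attached to V0 in one place and V1 in another. Two analysts could reach different adjusted results from the same data.

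The Background says a positive signal may guide a larger study, so a precise estimate of the Phase 1 effect is one of the main products of this pilot.

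**Working it through.** **Inputs.** The Power paragraph gives 30 per arm randomised, 10% attrition, 27 per arm completing, d = 0.9, two-sided 5% and power of 91.1%. The documents do not give the following, so they are assumed:

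- the V1–V2 correlation ρ (0.4, 0.6, 0.8);
- the ratio k = SD(V2)/SD(V1) (1 unless stated);
- the unit of d (change-score SD unless stated);
- the timing of losses (3 per arm, at random, all in Phase 1).

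**1. The plan's own figure.** By normal approximation, power = Φ(0.9 × √(27/2) − 1.96) = Φ(3.307 − 1.960) = Φ(1.347) = 0.911. This reproduces the stated 91.1%. The noncentral t with 52 df gives 90.1%.

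**2. Variance per child.** With SD(V1) = 1:

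- change score: 1 + k² − 2ρk
- ANCOVA on V1: k²(1 − ρ²)

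The two are equal only when the slope ρk is 1. At k = 1 the ratio ANCOVA/change is (1 − ρ²)/(2(1 − ρ)) = (1 + ρ)/2.

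| ρ | k = 0.8 | k = 1 | k = 1.25 |
|---|---|---|---|
| 0.4 | 0.5376/1.00 = 0.54 | 0.84/1.20 = 0.70 | 1.3125/1.5625 = 0.84 |
| 0.6 | 0.4096/0.68 = 0.60 | 0.64/0.80 = 0.80 | 1.00/1.0625 = 0.94 |
| 0.8 | 0.2304/0.36 = 0.64 | 0.36/0.40 = 0.90 | 0.5625/0.5625 = 1.00 |

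These are large-sample ratios. With 54 completers, estimating the slope costs about 2% in variance, so the break-even slope is about 0.96.

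**3. Completers only (27 per arm, k = 1).** The effect becomes d/√ratio, with noncentral t on 52 df (t-test) or 49 df (ANCOVA with V1 and two strata), ignoring the 2% cost. For ρ = 0.4, 0.6, 0.8:

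- d = 0.9: 90.1% to 97.2%, 95.2%, 92.7%
- d = 0.65: 65.0% to 79.9%, 74.5%, 69.4%

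**4. The planned analysis set (30 per arm, 3 per arm carried forward, k = 1).** With no ABC between V1 and V2, the value carried is V1. A tenth of the children therefore have V2 = V1, which pulls the slope to b = 0.9ρ + 0.1 = 0.46, 0.64, 0.82. The variance ratio is [0.9(1 + b² − 2bρ) + 0.1(1 − b)²] / [0.9 × 2(1 − ρ)]:

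- ρ = 0.4: 0.788/1.08 = 0.73
- ρ = 0.6: 0.590/0.72 = 0.82
- ρ = 0.8: 0.328/0.36 = 0.91

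Simulated ratios, which include the cost of estimating the slope, are 0.74, 0.83 to 0.84, and 0.93. So 60 children with ANCOVA match about 60/0.74 = 81, 60/0.83 = 72 and 60/0.93 = 65 with the t-test. Simulated power (100,000 trials per cell; ANCOVA with V1 and two balanced, non-prognostic strata):

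| | ρ = 0.4 | ρ = 0.6 | ρ = 0.8 |
|---|---|---|---|
| d = 0.9, t-test | 89.7% | 89.8% | 89.6% |
| d = 0.9, ANCOVA | 96.1% | 94.2% | 91.5% |
| d = 0.9, conditional rule | 90.6% | 90.3% | 89.8% |
| d = 0.65, t-test | 64.4% | 64.6% | 64.5% |
| d = 0.65, ANCOVA | 76.8% | 72.3% | 67.8% |
| d = 0.65, conditional rule | 65.1% | 65.1% | 64.7% |
| no effect, t-test | 5.2% | 5.2% | 4.9% |
| no effect, ANCOVA | 5.1% | 5.1% | 4.8% |
| no effect, conditional rule | 4.4% | 4.7% | 4.7% |

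The conditional rule here adjusts for V1 only if the arms differ on it at p < 0.05, which happens in 5.0–5.1% of trials. The 0.65 is illustrative. It is the top of the 0.42 to 0.65 range in the cited secondary analysis of risperidone trials on this subscale, a different drug.

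**5. Sensitivity (carried-forward set, d = 0.9; ρ = 0.4, 0.6, 0.8 except in the last line).**

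- k = 0.8: 89.7%, 89.4%, 89.6% rise to 98.6%, 97.6%, 97.2%.
- k = 1.25: 89.6%, 89.4%, 89.5% become 93.1%, 90.3%, 88.9%. In the last case the slope is 1 and ANCOVA loses a little.
- d = 0.9 in raw-score SDs, k = 1: 83.7%, 95.0%, 99.9% become 92.5%, 97.5%, 99.9%.
- ρ = 0.9, k = 1: 89.9% to 90.7%. At ρ = 0.95 there is no gain (89.9% against 89.8%).

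**The case against.** The planned primary test is simple, unbiased and fixed in advance, and it holds its type I error. At the plan's own target of d = 0.9 it already has about 90% power, and the study is described as exploratory and powered only for a large effect. The covariate rule affects only the follow-up analysis.

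The gain is also conditional on quantities nobody has supplied. The same parent form repeated after five weeks could correlate above 0.8. At 0.9 the gain is about 1 point, and with a slope of 1 ANCOVA loses roughly half a point to one point. Holding d fixed in change-score SDs while ρ varies means the three columns describe different raw effects: 0.9 × √1.2 = 0.99 raw SD at ρ = 0.4, but 0.9 × √0.4 = 0.57 at ρ = 0.8. A looser trigger would recover more: at p < 0.20, about 2.4 points at ρ = 0.4 and 1.6 at ρ = 0.6 (d = 0.9).

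All of this is correct, and it limits the size of the claim. It does not supply a reason to keep the slope at 1. The possible loss from ANCOVA is under one point, against possible gains of several points. Even the looser trigger recovers well under half of the gain, 2.4 of 6.4 points (96.1 − 89.7) at ρ = 0.4. Nor does the exploratory label settle what the covariate rule means.

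**Conclusion.** The concern holds as a matter of efficiency and prespecification. It is not a validity error, and the stated 91.1% power is reproduced. On the planned analysis set with equal SDs, d = 0.9 in change-score SDs and ρ from 0.4 to 0.8, prespecified adjustment is worth about 6, 4 and 2 points of power. At d = 0.65 it is worth about 12, 8 and 3 points. Across the SD ratios examined, the range at d = 0.9 runs from a loss of under one point to a gain of about 9 points. The exact value cannot be fixed, because the documents give neither the correlation nor the SDs. The covariate rule as written cannot be applied without further decisions. If it means p < 0.05, it recovers at most 0.9, 0.5 and 0.2 points. No precision gain is claimed for the stratification factors. The change is worth making but does not block the trial.

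**What to change.** Replace the primary analysis with an ANCOVA of V2 ABC-Social on treatment, with V1 ABC-Social, gender and the age/weight stratum recorded at randomisation all named in advance. Report the adjusted difference with its 95% confidence interval. State that baseline means V1. Use the same form for ABC-Stereotypic and the CSHQ score. Delete the rule that selects covariates by observed baseline difference. Keep the change-score t-test as a labelled sensitivity analysis.

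The stratum must be codable before it can be a covariate. As Treatment Randomization defines them, the Younger and Older groups each join an age limit and an 80 lb limit with the word or, so one child can meet both. The same grouping appears in Table 1. These passages must be reconciled and each child's assigned stratum recorded.

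The cost is one sentence in the Analysis section, no new data and about three degrees of freedom. Including the two strata costs about 0.1 point of power if they are not prognostic.
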